2.6.4.1 Tables and Figures

Tables:

- Primary treatment comparison for each of the 3 secondary endpoints: N events and patients, HR, 95% CI, log-rank test statistic and p-value, 5yr DFS, SE and 95% CI
- Sites of first failure, overall and by treatment group
- Types of second non-breast malignancies, as site of first failure, overall and by treatment group.
- Death without recurrence (list of patients with cause of death)

Figures:

- KM plots of BCFI, by treatment group, for entire analysis population (*y-axis: Percent Free from Breast Cancer; x-axis: Time since Randomization (12-month intervals); x-axis limited to 6 years (median survival plus 1 year) and numbers at risk at each 12-monthly interval*)
- KM plots of DRFI, by treatment group, for entire analysis population (*y-axis: Percent Free from Distant Recurrence; x-axis: Time since Randomization (12-month intervals); x-axis limited to 6 years (median survival plus 1 year) and numbers at risk at each 12-monthly interval*)
- KM plot of OS, by treatment group, for entire analysis population (*y-axis: Percent Alive; x-axis: Time since Randomization (12-month intervals); x-axis limited to 6 years (median survival plus 1 year) and numbers at risk at each 12-monthly interval*)

2.6.5 Adverse Events / Safety

2.6.5.1 Population

The toxicity population is the subset of patients in the ITT analysis population who started protocol treatment. Any patients without at least 1 post-baseline AE form submitted will not be able to contribute; note any such patients in trial report.

2.6.5.2 Analysis

Targeted AEs, and other grade 3-5 AEs, are collected on CRFs. The grade and causality attribution are recorded according to the NCI Common Terminology Criteria for Adverse Events (CTCAE) version 3.0.

The targeted AEs will be summarized by AE type and maximum grade over time, regardless of causality attribution. The maximum grade consolidates the reports of a given type of AE for a patient over time since randomization (i.e., baseline reports are excluded) by taking the maximum across time (i.e., a patient appears only once for a given type of AE). Patients with reports of multiple AEs of different types are reported multiple times under the relevant AE categories. Maximum grade 0 indicates that the AE type has not been reported.

2.6.5.3 Tables and Figures

Tables:

- Targeted AEs reported according to treatment group
- Targeted AEs reported according to prior endocrine therapy and treatment assignment
- Tables above repeated for the subset of events deemed possibly, probably or definitely related to study treatment(s)

Other grade 3 or higher AEs are also requested on CRFs, by write-in text. All will be tabulated, similarly according to max grade, but the intention is to focus on those deemed possibly, probably or definitely related to study treatment(s), which will also be tabulated.

95% exact CIs will be calculated for each targeted AE, according to treatment group.

The following late adverse events (LAEs) will be summarized descriptively in a table according to treatment group: cardiac ischemia/infarction, thrombosis/thrombus/embolism, CNS cerebrovascular ischemia, and fractures.

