## 9.2. Data analyses

The primary analysis will be undertaken with the intention-to-treat population of all randomized patients. The primary endpoint is disease-free survival (DFS: Section 6.1.1) and will be compared between treatment arms using a two-sided stratified logrank test with an overall experiment-wise alpha level equal to at most 0.05. Kaplan-Meier estimates of the DFS distributions will be calculated for each of the two treatment arms. Cox proportional hazards regression models will be used to investigate whether the treatment comparison is modified by adjustments for various covariates.

Other factors will be used to characterize the patients enrolled in the study and to provide descriptive statistics of outcomes according to subgroups of the population. These factors include age at randomization, body mass index, tumor size, tumor grade, number of positive lymph nodes, ER/PgR and HER2 status of the primary tumor, type of prior endocrine therapy, interval of time since the cessation of prior endocrine therapy. These analyses will be considered as secondary and descriptive.

The following secondary endpoints will be assessed: overall survival, distant disease-free survival, breast cancer-free interval, sites of first DFS failure, incidence of second (non-breast) malignancies, deaths without prior cancer event, incidence of targeted adverse events.

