1.2 TRIAL DESIGN

SOLE (IBCSG 35-07 / BIG 1-07) OVERVIEW

Title:	Study Of Letrozole Extension (SOLE): A phase III trial evaluating the role of continuous letrozole versus intermittent letrozole following 4 to 6 years of prior adjuvant endocrine therapy for postmenopausal women with hormone receptor positive, node-positive early stage breast cancer.
Patient Population:	Postmenopausal women who are disease-free following 4-6 years of prior adjuvant endocrine therapy with selective estrogen receptor modulator(s) (SERM) and/or aromatase inhibitor(s) (AI) for endocrine-responsive, node-positive early breast cancer.
Entry:	Patients must have stopped prior endocrine SERM/AI therapy, and must be randomized within 12 months (1 year) of the last dose of prior endocrine SERM/AI therapy.
Activation Date:	8 November 2007 (First patient randomized on 5 December 2007)
Target Accrual:	4800 patients
Closure Date:	12 July 2012 (Last patient randomized on 8 October 2012)
Final Accrual:	4884 patients

Trial Schema:

The SOLE trial is a multinational phase III randomized clinical trial designed to compare continuous letrozole for 5 years with intermittent letrozole over a 5-year period among postmenopausal women who are disease-free following 4 to 6 years of prior adjuvant endocrine therapy with SERM(s) and/or AI(s) for endocrine-responsive node-positive operable breast cancer. The hypothesis is that introducing 3 month treatment-free intervals during the course of 5 years of extended letrozole will improve disease-free survival.

The randomization was stratified according to participating center and prior SERM/AI endocrine therapy (SERM(s) alone, AI(s) alone, both SERM(s) and AI(s)). Patients were randomized 1:1 to one of two extended adjuvant endocrine therapy groups:

A: Continuous letrozole 2.5 mg daily for 5 years

B: Intermittent letrozole 2.5 mg daily for the first 9 months of years 1 through 4, with treatment-free intervals for the last 3 months of years 1 through 4, followed by 12 months of letrozole 2.5 mg daily in year 5

Patients should start trial treatment as soon as possible after randomization. Trial treatment should begin no later than 6 weeks from the date of randomization. All patients will be followed every 6 months for years 1 to 5, and yearly thereafter for assessment of disease status and for survival data collection.

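### Targeted adverse events get a separate exact interval in each arm but no between-arm estimate, so the plan never estimates the treatment contrast for this secondary endpoint (minor)

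*SAP*

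**What the plan says.** Protocol 9.2 includes "incidence of targeted adverse events" in its list of secondary endpoints to be assessed. It names no method for them.

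SAP 2.6.5.1 defines who is counted: "The toxicity population is the subset of patients in the ITT analysis population who started protocol treatment". SAP 2.6.5.2 sets the summary: "The targeted AEs will be summarized by AE type and maximum grade over time, regardless of causality attribution". Each patient counts once per AE type, so the quantity is a patient-level proportion in each arm.

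SAP 2.6.5.3 lists the main table as "Targeted AEs reported according to treatment group", with further tables by prior endocrine therapy and for treatment-related events. It then adds the only inferential statement in the section: "95% exact CIs will be calculated for each targeted AE, according to treatment group". Late AEs are summarized descriptively.

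Neither document gives a between-arm AE estimate anywhere else. SAP 2.6.4 extends the DFS-style comparison to BCFI, DRFI and OS only.

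**The concern.** The trial randomizes women to two letrozole schedules in order to compare them. For AEs, the quantity that answers that question is the difference (or ratio) in incidence between arms, with its uncertainty. The plan attaches uncertainty to something else, the rate within each arm.

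Two intervals printed side by side invite comparison by eye. Two 95% intervals can overlap while the interval for their difference clearly excludes zero, so that comparison is much stricter than the usual 5% level. Arm B is off letrozole for 3 months in each of years 1 to 4, so whether fractures, musculoskeletal symptoms or hot flashes differ by schedule is an obvious question for these tables. A moderate true difference could be read as none. A contrast chosen only after the results are known would also be less credible than one written into the SAP.

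**Working it through.** The AE section states no power, level or margin, so there is no planned figure to reproduce. The check is how an eye comparison of the planned intervals behaves against an interval for the difference.

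**Inputs**
- Patients: "4884 patients" randomized 1:1 (SAP 1.2), so 4884 / 2 = 2442 per arm. The size of the toxicity population is not given. I assume about 2,400 per arm; results at 2,300 and 2,442 are nearly the same.
- Exact is taken to mean Clopper-Pearson.
- Illustrative rates from Protocol 5.2.1: bone fractures 5.7% v 4% (letrozole v tamoxifen, adjuvant), arthralgia/arthritis 28.7% and hot flashes 49.7% (extended adjuvant). They come from other trials and serve only to fix the scale.

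**Level of the overlap comparison**

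With equal standard errors s, two 95% intervals separate when the difference exceeds 2 × 1.96 × s. The standard error of the difference is √2 × s. So separation needs |z| > 2 × 1.96 / √2 = 2.77, two-sided p = 0.0056.

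Exact enumeration of Clopper-Pearson intervals over two binomials, n = 2442 per arm and equal true rates, gives the probability of non-overlap:

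| True rate | P(no overlap) |
|---|---|
| 0.5% | 0.0028 |
| 5.7% | 0.0046 |
| 28.7% | 0.0051 |
| 49.7% | 0.0053 |

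That is about 0.005 for common AEs, and lower for rare ones.

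**Smallest observed difference that shows (n = 2,400 per arm, second arm higher)**

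| Base rate | Difference CI excludes 0 | Arm CIs separate | p at first separation |
|---|---|---|---|
| 5% | 1.3 points | 2.0 points | 0.004 |
| 20% | 2.3 | 3.4 | 0.005 |
| 29% | 2.6 | 3.8 | 0.005 |
| 50% | 2.8 | 4.0 | 0.005 |

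The difference CI here is the Wald interval; at these sample sizes the choice of method hardly matters.

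**Probability of showing a true difference (n = 2,400 per arm)**

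| True rates | Difference CI | Non-overlap |
|---|---|---|
| 29% v 32.5% | 75% | 43% |
| 29% v 25.5% | 78% | 47% |
| 29% v 24% | 98% | 87% |
| 49.7% v 43.3% | 99% | 95% |
| 1.2% v 0.9% | 17% | 3% |

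Normal-theory check for the first row: the arm standard errors are 0.00926 and 0.00956, and that of the difference is 0.01331. Then z = 0.035 / 0.01331 = 2.63, and Φ(2.63 − 1.96) = 0.75. Non-overlap needs 1.96 × (0.00926 + 0.00956) / 0.01331 = 2.77, and Φ(2.63 − 2.77) = 0.44, close to the exact 43%.

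**Worked example**

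Take 139 v 98 fractures of 2442 (5.7% v 4.0%). The planned exact intervals are 4.8 to 6.7% and 3.3 to 4.9%, which overlap. The difference is 1.7 points, 95% CI 0.5 to 2.9 (the same to one decimal by Wald or Newcombe), p = 0.006.

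**The case against.** The strongest reply is that the SAP plans no AE test and sets no overlap rule. A reader might infer that targeted AEs are to be tested at about 0.005, or that the plan conceals safety differences. The documents support neither. The 0.005 describes what happens if someone compares the intervals by eye. The per-arm counts and denominators are tabulated, so anyone can work out the difference from them. This part stands, and it limits the point to a gap in prespecified estimation.

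A descriptive reading of the AE section is also consistent with the documents: Protocol 9.2 names a test only for DFS, and the SAP says AEs will be summarized. That is fair, but a difference with its interval can be just as descriptive, and it describes the quantity the randomization was set up to compare.

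Three limits on size also stand:
- The two approaches part company only for moderate differences; at 29% v 24% or 49.7% v 43.3% both usually show the effect.
- Rare vascular events gain little. Protocol 5.2.1 gives 1.2% for thromboembolic events; a fall of a quarter, to 0.9%, would show with only 17% probability even with a difference CI.
- Lower toxicity is not a stated aim. The hypothesis is better DFS, and the other benefit argued is cost-effectiveness (Protocol 1.6). Symptoms may also be compared in the quality-of-life substudy (Protocol 10.2, Appendix III, not available here), but only some centers take part.

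**Conclusion.** The point holds as a minor one. For a named secondary endpoint of a randomized comparison, the plan gives intervals for each arm and no estimate of the contrast. If those intervals are compared by eye, the working level is about 0.005, and a 3.5-point increase from 29% is shown 43% of the time rather than 75%. A true difference that a direct comparison would detect with 80% power has about 49 to 50% under non-overlap (for example 5.7% v 4.0% or 28.7% v 25.1%, n = 2442 per arm).

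This rests on about 2,400 treated women per arm, on Clopper-Pearson intervals, and on AE rates borrowed from other trials. In those trials the comparator was tamoxifen or placebo, whereas both arms here take letrozole, so the differences actually seen may be smaller. The DFS analysis is not affected, and no data are lost.

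**What to change.** In SAP 2.6.5.3, keep the per-arm exact intervals and add text along these lines: In the main table of targeted AEs by treatment group, the Arm B minus Arm A difference in incidence will be given for each targeted AE with a 95% CI (Newcombe or Miettinen-Nurminen, one method named in advance), for any grade and for grade 3 or higher. These intervals are descriptive and are not adjusted for multiplicity.

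The descriptive label belongs in the SAP text itself. Confining the addition to the main table avoids multiplying intervals across the prior-therapy and treatment-related tables.

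Cost: a short addition to the SAP and the added difference columns in one table, with no new data. The downside is the number of intervals. The legend to Protocol Table 7.1 names 13 targeted AEs, so 13 × 2 = 26. If no AE truly differed, about 26 × 0.05 = 1.3 would exclude zero by chance, and under independence the chance of at least one is 1 − 0.95^26 = 74%. AEs are correlated, so the 74% is only a rough guide, but it is the reason for the label.

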#### Legend to Table 7.1

- A. The day of randomization is considered Day 0 for the purpose of follow-up.
- B. Biochemical evidence of definite postmenopausal status, defined as estradiol, FSH, and LH in the postmenopausal range, is required at study entry for some patients as defined in section 3.1.1.
- C. Adverse events should be graded using the NCI CTCAE V.3 (Appendix II). The following targeted adverse events should be recorded on the CRF during the reporting period in which they occur:
  - Hot flashes/flushes
  - Osteoporosis

- Bone fracture
- Musculoskeletal symptoms (myalgia, arthralgia (joint pain), stiffness not including bone fractures)
- Mood alteration / depression
- Hypertension
- Cardiac ischemia/infarction
- Thrombosis / thrombus / embolism
- CNS cerebrovascular ischemia
- Hemorrhage, CNS
- Insomnia
- Fatigue
- Bone pain
- Other Grade 3 or higher adverse events

- D. Late adverse events (adverse events occurring after trial treatment is completed) should be recorded on Follow-up Form (E).
- E. Hematology is recommended within 2 months prior to randomization and should be done whenever medically indicated.
- F. Blood chemistry (includes liver function tests with alkaline phosphatase) is recommended within 2 months prior to randomization and should be done whenever medically indicated.

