## 7.2. Adverse event reporting

The main criterion for tolerability is the occurrence of toxicities and adverse events. The severity and causality will be classified according to the NCI CTCAE Version 3.0. The CTCAE is available for downloading on the internet at (<http://ctep.cancer.gov/reporting/ctc.html>).

An adverse event is defined as any untoward medical occurrence that occurs from the first dose of study medication until 30 days after the final dose, regardless of whether it is considered related to a medication.

In addition, any known untoward event that occurs subsequent to the adverse event reporting period that the investigator assesses as possibly related to the protocol treatment should be considered an adverse event.

Symptoms of the targeted cancer (if applicable) should not be reported as adverse events.

The adverse event severity grade provides a qualitative assessment of the extent or intensity of an adverse event, as determined by the investigator or as reported by the subject. The severity grade does not reflect the clinical seriousness of the event, only the degree or extent of the affliction or occurrence (e.g. severe nausea, mild seizure), and does not reflect the relationship to study drug.

Severity grade for other adverse events, not covered in the toxicity grading scale:

1 = Grade 1	Mild
2 = Grade 2	Moderate
3 = Grade 3	Severe
4 = Grade 4	Life-threatening
5 = Grade 5	Fatal

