### 8.1. Case report forms schedule

RANDOMIZATION FORMS		
Informed Consent Form	Consent to participation in clinical trial	Obtain before randomization and keep with patient records.
Pathology material consent	Consent to submission of pathology material	Obtain before randomization and keep with patient records.
Form PMC	Pathology Material Consent Form	DataFax after randomization with Form 35-A.
Form 35-A	Confirmation of Registration Form	Fill in before contacting your Randomization Center or entering the IBCSG Registration/Randomization system to randomize. DataFax completed form for all patients randomized.
BASELINE FORMS		
Form 35-H	History Form	DataFax within 1 month of randomization.
Pathology Report	Pathology Report of original diagnosis	DataFax within 1 month of randomization. See Section 10 for pathology material requirements.
Form 35-AE	Adverse Event Form	Complete prior to starting protocol treatment (letrozole) and DataFax within 1 month of randomization. This form is also required at follow-up (see instructions below).
Form 35-CCM	Concomitant Medications Form	Complete prior to starting protocol treatment (letrozole) and DataFax within 1 month of randomization. This form is also required at follow-up (see instructions below).
FOLLOW-UP FORMS		
Form 35-E	Follow-Up Form	DataFax every 6 months during Years 1-5, and yearly until death.
Form 35-L	Letrozole Form	DataFax at each follow-up period until the completion of letrozole.
Form 35-AE	Adverse Event Form	DataFax at each follow-up period during protocol therapy (letrozole). This form is also required at baseline.
Form 35-CCM	Concomitant Medications Form	DataFax at each follow-up period during protocol therapy (letrozole). This form is also required at baseline.
EVENT-DRIVEN FORMS		
Form 35-SAE-A	Serious Adverse Event Form (A)	DataFax within 24 hours when SAE occurs, see Section 7.3.
Form 35-SAE-B	Serious Adverse Event Form (B)	DataFax within 15 days of the initial report and/or at the definitive SAE outcome, see Section 7.3.

The Data Managers' Manual for this trial contains instructions for submitting forms using the DataFax system.

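### The documents do not settle whether adverse event recording ends with letrozole or at month 60, and SAP 2.6.5 plans no fracture or vascular comparison that is protected if early stopping differs by arm

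*SAP*

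**What the plan says.** **Collection.** Protocol 8.1 requires the Adverse Event Form at baseline and then "DataFax at each follow-up period during protocol therapy (letrozole". Protocol 7.2 defines an adverse event as one occurring "from the first dose of study medication until 30 days after the final dose"; a later event counts only if the investigator thinks it possibly related to treatment. Note D in the legend to Table 7.1 says: "Late adverse events (adverse events occurring after trial treatment is completed) should be recorded on Follow-up Form (E". That note has no relatedness condition. Form E is due "DataFax every 6 months during Years 1-5, and yearly until death".

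**Visit schedule.** Table 7.1 marks adverse events as mandatory at every visit from baseline to month 60, with no exception for patients who have stopped letrozole. Late adverse events appear only in the yearly column after month 60.

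**Analysis.** SAP 2.6.5.1 takes as its population the ITT patients who started treatment. SAP 2.6.5.2 states: "The maximum grade consolidates the reports of a given type of AE for a patient over time since randomization (i.e., baseline reports are excluded". This fixes the start of the window but not its end. SAP 2.6.5.3 adds "95% exact CIs will be calculated for each targeted AE, according to treatment group". It then lists a separate late-event table for cardiac ischemia or infarction, thrombosis or embolism, CNS cerebrovascular ischemia and fractures: "The following late adverse events (LAEs) will be summarized descriptively in a table according to treatment group". No denominator or observation period is given for that table. SAP 2.6.5 lists no output that merges the two sources, measures time to first event, adjusts for observation time, or estimates a difference between arms.

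**The concern.** Fracture and the vascular events are serious harms on which a continuous and an intermittent schedule of the same drug could plausibly differ. Protocol 5.2.1 itself reports more fractures on letrozole than on tamoxifen in the adjuvant setting (5.7% v 4%).

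A crude proportion is comparable between arms only if both arms are observed for similar lengths of time. If the Adverse Event Form stops when letrozole stops, each patient's window in the main table is roughly her own treatment duration. The assignment is reported to the center (Protocol 4.2) and no placebo is described, so the decision to stop can depend on the arm. SAP Table 2.6.6.1 lists adverse event and patient decision among the reasons for early stopping, so the end of the window may also be related to tolerability.

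Reading the main and late tables side by side does not recover a common window. One patient can appear in both, so the counts cannot simply be added.

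**Working it through.** **Step 1. Which rule sets the end of the window?**

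| Source | After an early stop, adverse events are recorded |
|---|---|
| Protocol 8.1 | Not on the Adverse Event Form |
| Protocol 7.2 | To 30 days after the last dose; later only if possibly related |
| Legend to Table 7.1, note D | On Form E, once trial treatment is completed; no relatedness limit |
| Table 7.1 | At every visit to month 60; late events only after that |
| SAP 2.6.5.2 | Since randomization; no end stated |

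For a patient who completes five years these nearly agree. For one who stops at, say, year 2, they do not.

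**Step 2. What follows if Protocol 8.1 governs?** The documents give no figure to reproduce, so this is an illustration.

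Inputs:
- True 5-year fracture risk 5.7% in both arms. The percentage is in Protocol 5.2.1; treating it as a 5-year risk is an assumption (3% and 10% were also tried).
- Early stopping by 5 years, S, of 20%, 30% or 40%. Assumed.
- Constant event hazard h and exponential time to stopping with rate m. Assumed.
- Grace period d = 30/365.25 = 0.0821 years, from Protocol 7.2.

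Formulas: h = −ln(1 − 0.057)/5 = 0.01174 per year and m = −ln(1 − S)/5. The on-treatment probability, with the window ending at the earlier of stop + d and 5 years, is

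p_on = (1 − e^(−hd)) + e^(md) × h/(h + m) × (e^(−(h+m)d) − e^(−5(h+m))).

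- S = 40%: m = 0.1022; p_on = 0.00096 + 1.0084 × 0.1031 × (0.9907 − 0.5658) = 4.51%. The late part within 5 years is 5.70 − 4.51 = 1.19%.
- S = 20%: m = 0.0446; p_on = 0.00096 + 1.0037 × 0.2082 × (0.9954 − 0.7544) = 5.13%. The late part is 0.57%.

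| Stop early, A v B | On-treatment, A v B | Ratio B/A | Late ratio B/A | Fixed 5-year window, ratio |
|---|---|---|---|---|
| 20% v 20% | 5.13% v 5.13% | 1.00 | 1.00 | 1.00 |
| 30% v 20% | 4.83% v 5.13% | 1.06 | 0.65 | 1.00 |
| 40% v 20% | 4.51% v 5.13% | 1.14 | 0.48 | 1.00 |
| 20% v 40% | 5.13% v 4.51% | 0.88 | 2.10 | 1.00 |

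The ratios are practically unchanged at a 3% or 10% risk.

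**Step 3. Could it hide a real difference?** Take a true hazard ratio (B/A) of 0.85, which gives a 5-year risk ratio of 0.854. With 40% (A) v 20% (B) stopping, the on-treatment table expects 4.51% v 4.38%, a ratio of 0.97.

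**Step 4. Size against sampling error.** With 4,884/2 = 2,442 patients per arm and a mean proportion of 4.82%, the SE of the difference is √(2 × 0.0482 × 0.9518/2442) = 0.61 percentage points. The 40% v 20% distortion is 5.13 − 4.51 = 0.62 points, about one SE.

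**The case against.** The strongest reply is that the main table may already be close to a common window. Table 7.1 requires adverse events to month 60 and puts late events only after it. Note D speaks of treatment being completed, and SAP Table 2.6.6.1 separates completing treatment from stopping early. SAP 2.6.5.2 counts from randomization without ending at the stop. On that reading both arms are split near month 60. This stands to the extent that a reader who infers that the main table is an on-treatment table, or that the arms are never compared over the same period, goes beyond the documents. It does not remove the point, because Protocol 8.1 and 7.2 say otherwise for early stoppers and the SAP does not choose.

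A reader might also infer that the arm stopping earlier will simply look safer. That holds only for the on-treatment table; the late table moves the other way, and both are reported by arm.

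It is also fair that the planned treatment span is five years in both arms, that allocation is 1:1, and that the administrative cut-off affects both arms alike. Only differential stopping creates a distortion. SAP 2.6.6 will show treatment termination curves and days on treatment by arm, so readers could see unequal exposure. Those displays would reveal a problem but would not correct the event comparison. Deaths are compared from randomization through overall survival, but non-fatal fractures and vascular events are not covered by that.

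**Conclusion.** The point holds in conditional form. The protocol passages disagree on how long, and on which form, adverse events are recorded after an early stop, and the SAP leaves this open while summarizing the two sources in separate crude tables. If form collection follows treatment and stopping differs by arm, both tables are distorted, in opposite directions.

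The size is unknown. It is zero with equal stopping. With assumed stopping rates of 20% and 40%, the on-treatment ratio shifts by roughly 12% to 14%, about one standard error of the difference in this trial. The late ratio shifts further, on much smaller percentages. These figures rest on assumed risks, constant hazards and assumed stopping rates. They show what could happen and do not predict what this trial will show. Adverse events are a secondary endpoint and the primary analysis is untouched.

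**What to change.** 1. **Reconcile the protocol passages** (Table 7.1, its note D, 7.2 and 8.1). State how long and on which form adverse events are recorded after an early stop, and whether post-treatment reports are all-cause or only those judged possibly related. State the resulting end of window for the targeted event tables in SAP 2.6.5.2.
2. **Add one analysis to SAP 2.6.5.3** for fracture, cardiac ischemia/infarction, thrombosis/embolism and CNS cerebrovascular ischemia. Combine Adverse Event Form and Form E reports. For each type, report cumulative incidence of first event from randomization to data cut-off, by assigned arm in the toxicity population and regardless of treatment status. Treat death as a competing event, and give a pre-named between-arm estimate with its 95% CI. If onset dates are not recorded, time events by reporting period.
3. **Keep the existing on-treatment and late-event tables** as supportive, each labelled with its observation window.

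Cost: SAP wording, one combined table and minor work to remove events reported on both forms. Form E is already submitted throughout follow-up, so a data route appears to exist. The documents do not show the forms themselves, however. If Form E captures these events less completely than the Adverse Event Form, or only when judged related, the combined result needs a caveat to that effect.
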